#### **11.1.5. Dissemination of Clinical Study Data**

- Where required by applicable regulatory requirements, an investigator signatory will be identified for the approval of the clinical study report. The investigator will be provided reasonable access to statistical tables, figures, and relevant reports and will have the opportunity to review the complete study results at a GSK/ViiV site or other mutually-agreeable location.
- GSK/ViiV will also provide the investigator with the full summary of the study results. The investigator is encouraged to share the summary results with the study participants, as appropriate.

- The procedures and timing for public disclosure of the protocol and results summary and for development of a manuscript for publication for this study will be in accordance with GSK Policy.
- GSK/ViiV intends to make anonymized participant-level data from this trial available to external researchers for scientific analyses or to conduct further research that can help advance medical science or improve patient care. This helps ensure the data provided by trial participants are used to maximum effect in the creation of knowledge and understanding

#### **11.1.6. Data Quality Assurance**

- All participant data relating to the study will be recorded on printed or electronic CRF unless transmitted to the sponsor or designee electronically (e.g., laboratory data). The investigator is responsible for verifying that data entries are accurate and correct by physically or electronically signing the CRF.
- The investigator must maintain accurate documentation (source data) that supports the information entered in the CRF.
- The investigator must permit study-related monitoring, audits, IRB/IEC review, and regulatory agency inspections and provide direct access to source data documents.
- Monitoring details describing strategy (e.g., risk-based initiatives in operations and quality such as Risk Management and Mitigation Strategies and Analytical Risk-Based Monitoring), methods, responsibilities and requirements, including handling of noncompliance issues and monitoring techniques (central, remote, or on-site monitoring) are provided in the Monitoring Plan.
- The sponsor or designee is responsible for the data management of this study including quality checking of the data.
- The sponsor assumes accountability for actions delegated to other individuals (e.g., Contract Research Organizations).
- Study monitors will perform ongoing source data verification to confirm that data entered into the CRF by authorized site personnel are accurate, complete, and verifiable from source documents; that the safety and rights of participants are being protected; and that the study is being conducted in accordance with the currently approved protocol and any other study agreements, ICH GCP, and all applicable regulatory requirements.
- Records and documents, including signed ICF, pertaining to the conduct of this study must be retained by the investigator for 15 years from the issue of the final Clinical Study Report (CSR)/ equivalent summary unless local regulations or institutional policies require a longer retention period. No records may be destroyed during the retention period without the written approval of the sponsor. No records may be transferred to another location or party without written notification to the sponsor.

### **11.1.7. Source Documents**

- Source documents provide evidence for the existence of the participant and substantiate the integrity of the data collected. Source documents are filed at the investigator's site.
- Data reported on the CRF or entered in the eCRF that are transcribed from source documents must be consistent with the source documents or the discrepancies must be explained. The investigator may need to request previous medical records or transfer records, depending on the study. Also, current medical records must be available.
- Definition of what constitutes source data can be found in Monitoring Plan.

### **11.1.8. Study and Site Start and Closure**

The study start date is the date on which the clinical study will be open for recruitment of participants.

The first act of recruitment is the first site open and will be the study start date.

GSK/ViiV or its designee reserves the right to close the study site or terminate the study at any time for any reason at the sole discretion of GSK/ViiV. Study sites will be closed upon study completion. A study site is considered closed when all required documents and study supplies have been collected and a study-site closure visit has been performed.

The investigator may initiate study-site closure at any time, provided there is reasonable cause and sufficient notice is given in advance of the intended termination.

Reasons for the early closure of a study site by the sponsor or investigator may include but are not limited to:

- Failure of the investigator to comply with the protocol, the requirements of the IRB/IEC or local health authorities, the sponsor's procedures, or GCP guidelines
- Inadequate recruitment of participants by the investigator
- Discontinuation of further study intervention development

If the study is prematurely terminated or suspended, the sponsor shall promptly inform the Investigators, the IECs/IRBs, the regulatory authorities, and any contract research organization(s) used in the study of the reason for termination or suspension, as specified by the applicable regulatory requirements. The Investigator shall promptly inform the participant and should assure appropriate participant therapy and/or follow-up, if required.

### **11.1.9. Publication Policy**

- The results of this study may be published or presented at scientific meetings. If this is foreseen, the investigator agrees to submit all manuscripts or abstracts to the sponsor before submission. This allows the sponsor to protect proprietary information and to provide comments.

- The sponsor will comply with the requirements for publication of study results. In accordance with standard editorial and ethical practice, the sponsor will generally support publication of multicenter studies only in their entirety and not as individual site data. In this case, a coordinating investigator will be designated by mutual agreement.
- Authorship will be determined by mutual agreement and in line with International Committee of Medical Journal Editors authorship requirements.

## 11.2. Appendix 2: Clinical Laboratory Tests

- The tests detailed in [Table 3](#) will be performed by the local laboratory.
- Protocol-specific requirements for inclusion or exclusion of participants are detailed in Section [5](#) of the protocol.
- Additional tests may be performed at any time during the study as determined necessary by the investigator or required by local regulations.
- Pregnancy Testing
  - Refer to Section [5.1](#) Inclusion Criteria for screening pregnancy criteria.
  - Pregnancy testing (urine or serum as required by local regulations) should be conducted per SoA.
  - Additional serum or urine pregnancy tests may be performed, as determined necessary by the investigator or required by local regulation, to establish the absence of pregnancy at any time during the participant's participation in the study.

**Table 3 Protocol-Required Safety Laboratory Assessments**

Laboratory Assessments 	Parameters				
Hematology	Platelet Count	RBC Indices: Mean Corpuscular Volume Mean Corpuscular Hemoglobin %Reticulocytes		White Blood Cell count with Differential: Neutrophils Lymphocytes Monocytes Eosinophils Basophils	
	Red blood cell (RBC) Count				
	Hemoglobin				
	Hematocrit				
Clinical Chemistry 	Blood Urea Nitrogen	Potassium		Aspartate Aminotransferase (AST)/ Serum Glutamic-Oxaloacetic Transaminase (SGOT)	Total and direct bilirubin
	Creatinine	Sodium		Alanine Aminotransferase (ALT)/ Serum Glutamic-Pyruvic Transaminase (SGPT)	Total Protein
	Glucose fasting	Calcium		Alkaline phosphatase	
Coagulation tests	Prothrombin Time		Partial Thromboplastin Time	International Normalized Ratio	

Laboratory Assessments 	Parameters
Routine Urinalysis	
 
• Specific gravity
 
• pH, glucose, protein, blood, ketones by dipstick
 
• Microscopic examination (if blood or protein is abnormal)
 

Other Screening Tests	
 
• HIV: HIV 1-2 antibody/antigen (Ab/Ag) testing
 
• Hepatitis B screen: Hepatitis B surface antigen (HBsAg)
 
• Hepatitis B surface antibody(HBsAb), and Hepatitis core antibody (HBcAb)
 
• Hepatitis C (Hep C antibody)
 
• Alcohol screen and drugs of abuse screen (to include at minimum: amphetamines, barbiturates, cocaine, opiates, cannabinoids and benzodiazepines)
 
• Urine (or serum) human Chorionic Gonadotropin Pregnancy test (as needed for women of child bearing potential)
 
 
The results of each test must be entered into the CRF.

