#### 1.3.1. Screening and Oral Lead-in Phase

Study Period	Screening 	Oral Lead-in 			Day 29	Early Withdrawal 	Washout Period
		Dosing Days 1-28					
Visit Window	Within 30 days of oral lead-in	Day -1	Day 1	Day 2	Day 14	Within 24 hours of the Day 28 last dose	EW
Informed Consent	X						10 – 14 days
Demographics	X						
Medical / Medication / Drug / Alcohol History	X						
Inclusion/Exclusion Criteria 	X	X					
Height, Weight, BMI	X						
Physical Exam	X	X					
Vital Signs 	X	X	X	X	X	X	
12-Lead ECG	X	X			X		
Drug / Alcohol Screen 	X	X					

Study Period	Screening 		Oral Lead-in 			Day 29	Early Withdrawal 	Washout Period
			Dosing Days 1-28					
Visit Window	Within 30 days of oral lead-in	Day -1	Day 1	Day 2	Day 14	Within 24 hours of the Day 28 last dose	EW	10 – 14 days
Pregnancy Test 	X		X		X	X		
Testing for SARS-CoV-2 	X	X						
Hepatitis B, Hepatitis C Screening	X							
HIV Test	X							
Urine Dipstick	X							
Hematology with differential; Clinical Chemistry Tests 	X		X	X	X	X	X	
Coagulation Tests	X							
Admit to clinic		X						
Dispense Oral lead-in IP			X					
Administer oral CAB + RPV 			X	X	X			
Dispense Medication Dosing Diary				X				
Drug accountability/ pill count/review drug diary				X	X	X		
Blood plasma PK sampling 			X	X	X	X	X	
AE Assessment 			X	X	X	X	X	
Concomitant Medication Review			X	X	X	X	X	
Genetic sample 			X					
Discharge from the clinic				X				

1. Screening may occur over more than one visit but within 30 days of the first dose of oral CAB and RPV in the oral lead in phase.

2. Eligibility criteria must be carefully assessed at the Screening visit and confirmed at the Day 1 Oral lead-in phase visit and re-confirmed prior to injection.
3. Prior to administering the first oral dose of CAB and RPV, study personnel must verify the following pre-dose assessments to be within normal limits prior to administration: vital signs, pregnancy test (negative; Females of Reproductive Potential (FRP) only. The results of the Drug/Alcohol screen, hematology with differential, and clinical chemistry tests on Day 1 are not required prior to administering the first oral doses of CAB and RPV but should be drawn prior to CAB and RPV administration.

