#### **4.1.2. Oral Lead-in Phase**

Participants that are eligible to participate will be admitted to the clinic on Day 1 of the OLI phase and receive their first oral dose of CAB 30 mg and RPV 25 mg with a standard breakfast after the completion of all pre-dose assessments. Participants will undergo sparse PK sampling of blood as described in Schedule of Activities (SoA). After a pre-dose 24-hour PK sample collection and laboratory assessments, participants will take their Day 2 study interventions with a meal at the clinic. Participants will be dispensed a sufficient supply of oral CAB + RPV tablets to complete 26 days of once daily dosing at home (with exception of the visit days at the clinic) and be counseled to take their dose with a meal at about the same time each day, before getting discharged on Day 2.

On Day 14 of the OLI phase, the participants will return to the clinic. A pre-dose PK sample will be collected. In addition, this visit will include assessment of safety, tolerability, and participant adherence to study drug. Participants should bring their supply of oral CAB + RPV to the Day 14 visit to have drug accountability performed. Participants will receive Day 14 dose at the clinic.

Participants will return to the clinic on Day 29, within 24 hours of last dose on Day 28 for PK, drug accountability, and all assessments performed as described in the SoA Section 1.3. The participants will begin a wash-out period of 10-14 days, during which no CAB and RPV will be administered.

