### **5.3. Lifestyle Considerations**

#### **5.3.1. Meals and Dietary Restrictions**

An overnight fast is preferred prior to screening laboratory assessments; however, a minimum of a 6 hour fast is acceptable. Otherwise, food and drink can be given ad libitum

throughout the course of the trial. At visits where participants will be in the clinic for multiple hours, meals will be provided by the study site (in the form of a boxed lunch or card for use at the site cafeteria).

Refrain from consumption of red wine, Seville oranges, grapefruit or grapefruit juice, pomelos, exotic citrus fruits, grapefruit hybrids, or fruit juices during the oral lead in phase through Day 29 PK collection.

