# **7. DISCONTINUATION OF STUDY INTERVENTION AND PARTICIPANT DISCONTINUATION/WITHDRAWAL**

## **7.1. Discontinuation of Study Intervention**

Participants may voluntarily withdraw from the study at any time and for any reason. Site investigators and study staff may withdraw participants before their scheduled termination visit for safety, behavioral, or administrative reasons, or if the participants are unable or unwilling to comply with study procedures. The reasons for withdrawals will be recorded in the participants' study records. If a participant withdraws from the study, he/she may request destruction of any samples taken, and the investigator must document this in the site study records.

During the oral lead-in period, early withdrawal on medical grounds will occur if the participant develops a Grade 3 or higher AE that is judged by the investigator to be related directly to the study product (see [Appendix 3](#) and [Appendix 4](#) for definitions and grading of severity of adverse events), or a participant develops a grade 3 or higher clinical significant laboratory abnormality (see Division of AIDS [DAIDS] table [Appendix 7](#) for grading) or any AE that is deemed clinically significant by the investigator and is judged by the investigator to be related directly to the study product.

For liver-related stopping criteria, please refer to Section [7.1.1](#).

If a participant receives the injections, they will be followed 52-weeks post the final injection per protocol for appropriate procedures, including blood plasma PK sampling, and safety evaluations, and will not be removed from the study for medical reasons, unless they refuse to continue participation.

[figure not shown]
During the oral lead in phase additional pre-specified reasons for discontinuing a participant from the study (or, at minimum, discontinuing administration of study product and continuing safety evaluations) include:

- Pregnancy (please see Section 8.2.5)
- Protocol deviation
- Non-compliance
- Participant withdraws consent
- Participant lost to follow-up
- Investigator discretion
- Sponsor discontinues study

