## NOTES:

1. An overnight fast is preferred prior to screening laboratory assessments; however, a minimum of a 6 hour fast is acceptable.
2. Details of liver chemistry stopping criteria and required actions and follow-up assessments after liver stopping or monitoring event are given in Section 7.1 and [Appendix 7](#) All events of  $ALT \geq 3 \times$  upper limit of normal (ULN) and bilirubin  $\geq 2 \times$  ULN ( $>35\%$  direct bilirubin) or  $ALT \geq 3 \times$  ULN and international normalized ratio (INR)  $>1.5$ , if INR measured, which may indicate severe liver injury (possible Hy's Law), must be reported as an SAE (excluding studies of hepatic impairment or cirrhosis).
3. Local urine testing will be standard for the protocol unless serum testing is required by local regulation or IRB/IEC.

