**Table 6 Baseline Parameter Specifications**

Phase	Parameter	Study Assessments Considered as Baseline	Baseline Used in Data Display
Oral Lead-in Phase	Laboratory results, Vital Sign results, ECG results 	OLI Baseline = last non-missing pre-dose assessment collected <= Date of first OLI dose	OLI Day 1
Injection Phase	Laboratory results, Vital Sign results (pre-dose), ECG results  (pre-dose), CCI scores	Injection Phase Baseline = assessment collected on the date of CAB + RPV injection	Injection Day 1
Follow-up Phase	Laboratory results, Vital Sign results (pre-dose), ECG results  (pre-dose)	Follow-up Phase Baseline = assessment collected on the date of CAB + RPV injection	Injection Day 1

1. Average of the triplicate assessments for quantitative assessments will be used as the baseline.

If time is not collected, Day 1 assessments are assumed to be taken prior to first dose of the respective phase. Unless otherwise stated, if baseline data is missing no derivation will be performed and baseline will be set to missing.

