3.23.	Safety	201584/primary_07/ T3.134	Summary of Seizure Adverse Events of Special Interest by System Organ Class and Preferred Term (Number of Subjects and Occurrences)		SAC
3.24.	Safety	201584/primary_07/ T3.137	Summary of Hepatic Safety Profile: Assessment of Risk of Hepatotoxicity Adverse Events of Special Interest by System Organ Class and Preferred Term (Number of Subjects and Occurrences)		SAC
Laboratory: Chemistry					
3.25.	Safety	LB1	Summary of Chemistry Changes from Baseline by Study Phase and Visit	ICH E3	SAC
3.26.	Safety	LB1	Summary of Chemistry Values by Study Phase and Visit	ICH E3	SAC
3.27.	Safety	LB16	Summary of Chemistry Results by Maximum Grade Increase Post-Baseline Relative to Baseline	ICH E3 Repeat for each study phase	SAC
Laboratory: Hematology					
3.28.	Safety	LB1	Summary of Hematology Changes from Baseline by Study Phase and Visit	ICH E3	SAC
3.29.	Safety	LB1	Summary of Hematology Values by Study Phase and Visit	ICH E3	SAC
3.30.	Safety	LB16	Summary of Hematology Results by Maximum Grade Increase Post-Baseline Relative to Baseline	ICH E3 Repeat for each study phase	SAC

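### Table 3 specifies fasting glucose, but only screening laboratory draws must be fasted, and the SAP summarises glucose change and worst grade without regard to fasting status

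*Protocol*

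**What the plan says.** Protocol Appendix 2, Table 3 names the glucose test "Glucose fasting" within clinical chemistry and does not restrict that label to any visit. Note 1 to the table, repeated in Section 5.3.1, is the only fasting instruction: "An overnight fast is preferred prior to screening laboratory assessments; however, a minimum of a 6 hour fast is acceptable". Section 5.3.1 continues: "Otherwise, food and drink can be given ad libitum".

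For OLI Day 1, note 3 to the Schedule of Activities says that chemistry samples "should be drawn prior to CAB and RPV administration". Section 4.1.2 has the first dose taken "with a standard breakfast after the completion of all pre-dose assessments".

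In SAP Table 6 the lead-in baseline is "OLI Baseline = last non-missing pre-dose assessment collected <= Date of first OLI dose". The baseline for both the injection and follow-up phases is the assessment on the day of injection. SAP Section 7.6 plans chemistry change from baseline by phase and visit, and the worst post-baseline grade by phase. The displays are Tables 3.25 to 3.27, the last being "Summary of Chemistry Results by Maximum Grade Increase Post-Baseline Relative to Baseline". None of these mentions fasting status.

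**The concern.** Glucose depends on recent food. The protocol names a fasting test but permits eating before every chemistry draw after screening, so the label and the collection rule do not agree. If the plan is followed as written, some values will come from fasted participants and some from fed ones, and no display will show which.

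Clinical laboratory tests are part of the stated safety endpoint. The study is open label with no concurrent control group, so the tables offer no comparison from which to judge whether a rise in glucose reflects the drug or a meal. Fasting status that is not recorded at the draw is hard to recover reliably afterwards.

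**Working it through.** The plan states no figure on this point, so there is nothing to reproduce. The check sets the passages side by side and then asks what can be said about size.

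**Food status by draw.** Lead-in draws are from the Schedule of Activities and Protocol Section 4.1.2. Later draws are from the laboratory windows in SAP Table 9. Baselines are from SAP Table 6.

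| Draw | Role | Food before the draw |
|---|---|---|
| Screening | OLI baseline only if Day 1 is missing | Fast of at least 6 h |
| OLI Day 1 | OLI baseline | Before dose and breakfast; no fast stated |
| OLI Day 2 | Post-baseline | Before that day's dose and meal; no fast stated |
| OLI Day 14 | Post-baseline | PK sample is pre-dose; timing of labs not stated |
| OLI Day 29 | Post-baseline | No clinic dose, no meal rule |
| Injection Day 1 | Baseline for injection and follow-up | No rule |
| Injection Days 8, 17, Week 4 | Post-baseline | No rule |
| Follow-up Weeks 8, 12, 24, 36, 52 | Post-baseline | No rule |

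**Mean change.** Let m be the average rise in glucose after a meal, f0 the share of participants fed at baseline and f1 the share fed at the later visit. The part of the mean change due to meals is

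m × (f1 − f0).

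- OLI Day 2: f0 and f1 are both probably near 0, so the artefact is near 0.
- OLI Day 29, and Day 14 if its labs are not drawn with the pre-dose PK sample: f0 is probably near 0 and f1 is unknown, so the artefact is about m × f1. It cannot be negative when f0 is 0.
- Injection and follow-up: f0 and f1 fall under the same food rule. If f1 = f0 the expected artefact is m × 0 = 0. If they differ, it can take either sign.

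Neither m, f0 nor f1 is given in the documents.

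**Worst grade.** Here several draws are set against one baseline, so equal fed shares do not remove the problem. SAP Sections 11.4.2 and 11.5.1 also bring unscheduled and off-target values into maximum-grade displays. Let q be the chance that a meal alone lifts one draw by a grade above baseline, with k draws per participant, n = 15 participants, and draws treated as independent. The chance of at least one spurious shift is

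1 − (1 − q)^(n × k).

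For the injection phase k = 3, so n × k = 45. All values of q are assumptions:

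- q = 0 gives 0.
- q = 1% gives 1 − 0.99^45 = 36%.
- q = 2% gives 1 − 0.98^45 = 60%.
- q = 10% gives 1 − 0.90^45 = 99%.

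The answer runs from none to almost certain depending on a quantity that the documents do not supply. It shows how the display is exposed and is not an estimate of the effect.

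**The case against.** The strongest reply is that this is a wording mismatch with little consequence. Several parts of that reply stand.

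- A fast is required only at screening, but other draws may be fasted in practice. OLI Day 1 and Day 2 labs precede the dosing meal, and Day 14 labs plausibly do.
- Protocol Section 8.1.4 refers to a laboratory manual, which is not among the documents. That manual or the CRF may already deal with fasting. If the manual required a fast after screening, it would conflict with Section 5.3.1, so reconciliation would still be needed.
- Glucose is one analyte in descriptive safety tables, and the sample is small enough that splitting it leaves few values per cell.

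Three stronger readings are tempting, and the documents do not support them.

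- *Glucose change is biased upward throughout the study.* This needs a fasted baseline and fed later draws. The injection-day baseline has no fasting rule, so a systematic shift does not follow in two of the three phases. Any figure in mmol/L would rest wholly on assumption.
- *Meals could lead to withdrawals.* The criterion in Protocol Section 7.1 applies in the oral lead-in and asks that "a participant develops a grade 3 or higher clinical significant laboratory abnormality". Nothing in the documents shows that a meal would produce a glucose value that is both Grade 3 and clinically significant, and Section 8.1.4 provides for repeat testing of clinically significant values.
- *The SAP grades every value as a fasting one.* The display titles do not say so, and the grading table in SAP Section 11.7.1 is not visible in the public version, so its treatment of glucose cannot be judged.

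What the reply does not answer is the visible conflict between Table 3 and Section 5.3.1, and the absence from both documents of any rule for recording or using fasting status.

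**Conclusion.** The point holds as a minor one. The protocol names a fasting analyte, requires a fast only at screening and allows food freely otherwise, while the SAP pools glucose values without regard to status.

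An upward meal artefact is possible at OLI Day 29 and perhaps Day 14, on the assumption that the Day 1 baseline is in practice pre-meal. In the injection and follow-up phases the likely effect is extra variability and occasional false worst-grade shifts, with no expected mean shift if fed shares are alike at baseline and later. The size cannot be derived from the documents. The primary PK endpoints are untouched.

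**What to change.** 1. In the protocol, reconcile Table 3 with Section 5.3.1 and Note 1: either state which laboratory visits are to be fasted, or relabel the analyte simply as glucose.
2. Record fasting status at each chemistry draw as yes or no, using at least 6 hours, which is the protocol's own minimum at screening. If the CRF already captures this, only the SAP needs changing.
3. In the SAP, flag glucose by status in the listings and in Tables 3.25 to 3.27, grade each value by the criteria that match its status, and show change from baseline for same-status pairs, as the primary or a supplementary display.

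The cost is one CRF field and the handling of one analyte. SAP Section 11.9 describes the display list as tentative until the full plan is written, so the change fits work still to come. The drawback is sparse cells: with about 15 participants, few same-status pairs may be available at a given visit. Keeping the all-values display alongside would limit that loss.
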